13.0 Risks to Participants

13.1 Foreseeable Risks: The study has the following risks:

- infection
- bleeding
- nerve injury
- cardiac arrhythmias (irregular heartbeat)
- respiratory complications

PROTOCOL TITLE: Prospective Randomized controlled study comparing liposomal bupivacaine to bupivacaine interscalene blocks for arthroscopic rotator cuff repair surgery

VERSION DATE: 8/5/2020

These complications all fall within the standard risks of surgery and the performance of the interscalene injection. Any intervention being provided as a part of this study falls within the standard of care as both medication options are within the standard treatments for post-operative pain and are currently used as analgesic options at UMMC.

EXPAREL contains bupivacaine. Serious side effects related to bupivacaine are not common, but may occur if too much is given or if it is accidentally injected into a blood vessel. When given incorrectly, side effects may involve the brain or the heart.

The effects on the brain and central nervous system may include:

- Restlessness (< 2%)
- Anxiety (<2%)
- Dizziness (<2%)
- Tinnitus (ringing in the ears) (<2%)
- Blurred vision (<2%)
- Tremors (shaking) possibly proceeding to convulsions (<2%).

The effects on the heart appear when too much bupivacaine is given or when bupivacaine is injected in a blood vessel by accident. These effects cause a decrease of the heart function, including low heart rate or abnormal heart rhythm, decreased blood flow, low blood pressure, and, in extreme cases, heart attack. (<2%)

The numbing sensation caused by bupivacaine may be persistent, with slow, incomplete, or no recovery. Sometimes a tingling sensation may appear in the area treated with bupivacaine. When injected next to a large nerve, bupivacaine may cause weakness or paralysis.

Allergic reactions are rare, but may include rash, itching and redness of the skin, sneezing, nausea, vomiting, dizziness, fainting, sweating, fever, and low blood pressure.

Other side effects of liposomal bupivacaine when given into the wound include:

PROTOCOL TITLE: Prospective Randomized controlled study comparing liposomal bupivacaine to bupivacaine interscalene blocks for arthroscopic rotator cuff repair surgery

VERSION DATE: 8/5/2020

- Nausea (22.6%)
- Constipation (8.7%)
- Vomiting (6%)
- High temperature (5.5%)
- Dizziness (<2%)
- Swelling (<1%)
- Low blood pressure (<2%)
- Anemia (<1%)
- Itching (2.4%)
- High heart rate (1.3%)
- Headache (5%)

13.2 Reproduction Risks:

If the patient were pregnant we would not perform the study on them. If they were to become pregnant there are no known risks to the patient.

13.3 Risks to Others: N/A

14.0 Potential Benefits to Participants

Potential Benefits: The potential benefits of participating in this study include reduced pain following shoulder surgery and shortened hospital stay.

15.0 Statistical Considerations

15.1 Data Analysis Plan: We plan to collect our data using excel, which will be maintained in box. When the study is completed and ready for statistical analysis the data will be shared with our staff statistician.

15.2 Power Analysis: Using the power analysis from our other ongoing interscalene block study (for total shoulder arthroplasty cases) we plan to continue to enroll to 70 total patients to reach an estimated 80% power.

15.3 Statistical Analysis: This study will be analyzed by our staff biostatistician. The data will be deidentified and shared with him in box. The statistician will be provided the protocol so they are able to analyze for primary and secondary objectives.

PROTOCOL TITLE: Prospective Randomized controlled study comparing liposomal bupivacaine to bupivacaine interscalene blocks for arthroscopic rotator cuff repair surgery

VERSION DATE: 8/5/2020

15.4 Data Integrity: All patients will be assigned a unique patient identifier. The data that will be sent to the statistician will be deidentified.

16.0 Confidentiality

16.1 Data Security: All paper documents and consent forms will be stored in a locked cabinet in the anesthesia research office in B573 Mayo. All study data will be stored electronically in Box and only the PI and members of the research team will have access to the data.

17.0 Provisions to Monitor the Data to Ensure the Safety of Participants

17.1 Data Integrity Monitoring.

The PI, co-investigators, and research assistants will all have access to the study data stored in the University's Box storage system. All the research assistants have experience collecting pain scores and other relevant study information. The PI of the study will periodically review the study data to ensure accuracy and completeness of study data.

17.2 Data Safety Monitoring: The Department of Anesthesiology has established a Data and Safety Monitoring Committee consisting of several staff anesthesiologists which include persons who are board certified as pain specialists. Data will be transmitted in box to persons on the board on a monthly basis for review. If there are patterns of adverse events, the board will meet as needed and provide recommendations.

All safety data will be collected on a case report form and transferred into an excel spread sheet that will be stored in box. Also, all phone call data will be collected on a case report form and transferred into excel in box.

All data will be collected by research assistants on a daily basis. Subjects are monitored at several intervals on day of surgery and daily up to 72 hours. If the patient is discharged prior to 72 hours they will Who will review the data.

The data will be reviewed on a regular basis (weekly) by the PI and research staff. If there are consistent complications noted a meeting will be convened by the DSMB for recommendations.

The statistical tests for analyzing the safety data to determine whether harm is occurring.

The statistician uses R or SAS for analysis. Most likely a regression analysis will be performed to see which event is most likely the contributor for the

PROTOCOL TITLE: Prospective Randomized controlled study comparing liposomal bupivacaine to bupivacaine interscalene blocks for arthroscopic rotator cuff repair surgery

VERSION DATE: 8/5/2020

complications Also a chi-square analysis can be performed. All is very dependent on data variability.

A fatal or serious adverse event that is attributable to either the delivery or the study medication itself.

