4.5 Biosafety: n/a

4.6 Stem Cells: n/a

5.0 Procedures Involved

5.1 Study Design: **Level I randomized prospective outcomes study comparing two groups of patients. One group will receive LB plus bupivacaine for an interscalene block. The other will receive bupivacaine for an interscalene block injection.**

Study Procedures: Patients will be identified in the pre-operative time period by the surgeons and if possible will be consented by the research coordinator or research assistant. If that is unable to be accomplished the patient will be introduced to the study and given a copy of the consent form to evaluate prior to surgery. On the day of surgery, the research coordinator, research assistant or primary or sub investigators will determine if the patient has any questions so that they can be answered. After discussion with the person obtaining consent, consent will be obtained in the pre-operative area. A random number generator will be used to determine if the patient will have LB plus bupivacaine or bupivacaine for their interscalene block. The primary investigator will access the number generator in the pre-op area immediately prior to block placement. The website www.random.org will be used as the random number generator.

Treatment technique:

All patients will receive preoperative oral multimodal medications consisting of acetaminophen 975 mg and gabapentin 300 mg.

After completion of the preoperative process the patient will be placed in the supine position with the head of the bed elevated 30 degrees with standard ASA monitors applied. Sedation will be provided with midazolam 0-2 mg and propofol 50 mg. The

PROTOCOL TITLE: Prospective Randomized controlled study comparing liposomal bupivacaine to bupivacaine interscalene blocks for arthroscopic rotator cuff repair surgery

VERSION DATE: 8/5/2020

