10.0 Local Number of Participants

10.1 Local Number of Participants to be Consented: 90 patients as we expect a dropout or loss to follow up of 20%

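### The regression in section 17.2 does not compare the randomised arms and cannot be relied on for toxicities listed at under 2%; neither it nor the optional chi-square bounds the risk

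*Combined protocol and SAP*

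**What the plan says.** Section 17.2 has a line that introduces "The statistical tests for analyzing the safety data to determine whether harm is occurring". Under it, the plan names R or SAS as software and then says "Most likely a regression analysis will be performed to see which event is most likely the contributor" to the complications. It continues: "Also a chi-square analysis can be performed. All is very dependent on data variability". The section names no treatment-arm term, safety endpoint, significance level, small-count rule or confidence interval.

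Nothing elsewhere fills the gap. Section 15 contains no safety analysis; section 15.3 says only that the statistician will receive the protocol and analyse the primary and secondary objectives. Yet the Study Summary lists adverse events among the secondary objectives, so section 17.2 is the only description of how they will be analysed.

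**The concern.** In a randomised trial, whether a treatment causes harm is judged by comparing the arms. A regression that asks which event contributes to the complications answers a different question. The alternative, chi-square, relies on a large-sample approximation that is doubtful when expected counts are small, and here most of them are.

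What is at stake is how the safety results will be read. A trial of this size will often see no cases of a rare toxicity. Without an interval, an empty table can pass for reassurance when the data still allow a substantial rate. And if the test is chosen after the data are seen, the choice can decide whether a difference is called significant.

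**Working it through.** **Inputs.**
- Sample size: section 15.2, "we plan to continue to enroll to 70 total patients to reach an estimated 80% power". Section 10.1 gives 90 to be consented, with 20% dropout; 70 / 0.80 = 87.5, so 88, which is close to 90.
- Allocation: section 5.1, "A random number generator will be used to determine if the patient will have LB plus bupivacaine or bupivacaine for their interscalene block". No ratio is stated. I assume 1:1, which gives 35 per arm of 70, or 45 per arm if all 90 are treated.
- Event rates: section 13.1. Central nervous system and cardiac effects are listed at under 2%; I use 2% as the ceiling. The higher rates are for liposomal bupivacaine given into the wound, and no control-arm rates are given, so counts based on them are indicative only.
- Two-sided 0.05 is my assumption; the plan states no level.

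The plan gives no expected safety counts, so there is no figure of its own to reproduce.

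**Step 1. Expected events per arm, n × p.**

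| Event (rate) | 35 per arm | 45 per arm |
|---|---|---|
| Listed at under 2% (ceiling 2%) | 0.70 | 0.90 |
| Itching (2.4%) | 0.84 | 1.08 |
| Headache (5%) | 1.75 | 2.25 |
| High temperature (5.5%) | 1.93 | 2.48 |
| Vomiting (6%) | 2.1 | 2.7 |
| Constipation (8.7%) | 3.0 | 3.9 |
| Nausea (22.6%) | 7.9 | 10.2 |

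An expected count of 5 needs a rate of 5/35 = 14.3% (5/45 = 11.1%). Only nausea reaches it.

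**Step 2. Can a regression be fitted for an event at 2%?** With 35 per arm:
- No event in a given arm: 0.98^35 = 0.493.
- No event in either arm: 0.98^70 = 0.243.
- At least one arm without an event: 1 − (1 − 0.493)² = 0.743.
- Three or fewer events among all 70 (binomial): 0.948.

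So even if an arm term were added, an ordinary logistic regression would have no finite arm estimate about three times in four. Otherwise it would usually rest on two or three events.

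**Step 3. What does chi-square do at these counts?** For 35 per arm:

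| Events | Uncorrected chi-square p | Fisher exact p |
|---|---|---|
| 4 v 0 | 0.039 | 0.114 |
| 5 v 0 | 0.020 | 0.054 |

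The tests disagree about significance. To see whether chi-square is too liberal, I enumerated all 2×2 tables with equal true rates in the arms. Uncorrected chi-square rejects in 0.5% of trials at 2%, 3.6% at 5%, 4.5% at 6%, 5.6% at 8.7% and 5.7% at 10%. It is therefore conservative at the rare rates and barely above 5% near 10%. For a true 2% v 10%, it rejects in 28% of trials and Fisher in 7%.

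**Step 4. What can the trial bound?** The exact two-sided 95% upper limit for 0 of n is 1 − 0.025^(1/n):
- 0/35: 10.0%.
- 0/45: 7.9%.
- 0/70 (arms pooled): 5.1%.

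The per-arm limit at 35 is twice the 5% in section 12.3, which does not say whether it applies by arm or overall.

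**The case against.** The strongest reply is that section 17.2 fixes nothing. Its wording is tentative and leaves the method to the data, which leaves room for an exact test. The chi-square is not said to ignore the arms, and a comparison by arm is its natural reading in a two-arm trial. This stands for the chi-square. It does not rescue the regression, whose stated purpose is to find a contributing event. Leaving the choice until the data are seen is itself a weakness when the candidate tests disagree as in step 3.

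A reader might also infer that chi-square would trigger false signals of harm. The enumeration does not support that: the rejection rate is 0.5% with equal 2% rates and about 5.7% near 10%. The 4 v 0 example shows two tests disagreeing, not that chi-square is the one in error. Nor do the documents tie safety action to a p-value: section 17.2 relies on weekly review, monthly data to the committee and meetings when patterns appear, and section 12.3 uses a percentage.

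A third inference is that fewer than one event per arm is expected for safety events generally. That holds for events listed at under 2%, but not for nausea, constipation or vomiting. Nausea and vomiting are among the complications to be recorded in section 5.1, and most other complications there have no stated rate.

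Finally, requiring Fisher would not be a free improvement. Falling from 28% to 7% power for 2% v 10% is a real loss where missed harm matters, so the choice of test is a trade-off.

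**Conclusion.** The point holds in a limited form. The regression as described does not compare the randomised arms, and for toxicities listed at under 2% it could not be estimated reliably, with at most 0.7 expected events per arm at 35 (0.9 at 45). The optional chi-square would face expected counts below 5 for every listed rate except nausea. Neither method bounds the risk, although 0/35 still allows 10.0%.

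The conclusion rests on 1:1 allocation, 35 to 45 per arm, 2% as the ceiling of the listed rates, and wound-use rates for the commoner events. It affects how safety results are reported and read. It does not touch the primary analysis, and no safety action in the documents depends on it. Severity is low.

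**What to change.** In section 17.2, replace the regression and chi-square sentences with wording such as: *For each complication, the number and percentage of patients affected will be given by randomised arm with exact 95% confidence intervals. The between-arm risk difference with a score or exact 95% confidence interval is the main safety summary. Any significance test is secondary.* Then name in advance the test to be used when expected counts are below 5. If Fisher is chosen, state its low power (about 7%, against 28% for uncorrected chi-square, at 2% v 10% with 35 per arm).

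The cost is a few sentences and no new data collection. The intervals will be wide, which is an honest picture of what a trial of this size can show about rare harm.

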18.0 Provisions to Protect the Privacy Interests of Participants

18.1 Protecting Privacy:

Patients will be asked if this is a good time to answer questions. All patients will have the right to refuse to answer questions when called. All calls will be done in a secure office and the data is deidentified when entered. It will be stored using a unique study identifier.

18.2 Access to Participants:

All patients are required to sign a consent that states their privacy of the data being collected. In addition, they are required to sign a HIPAA consent that further describes the data being collected. It also describes that all data is deidentified and stored in a secure database. They will be informed that data is stored and reviewed in box which is HIPAA compliant and that only study personnel have access.

19.0 Compensation for Research-Related Injury

19.1 Compensation for Research-Related Injury:

In the event that this research activity results in an injury, treatment will be available, including first aid, emergency treatment and follow-up care as needed. Care for such injuries will be billed in the ordinary manner, to the patient and/or insurance company.

19.2 Contract Language: N/A

20.0 Consent Process

- Consent Process (when consent will be obtained): Patients will be identified in the pre-operative time period by the surgeons and if possible will be consented by the research coordinator or research assistant. If patients have more questions and do not want to sign at their clinic will be asked if it is allowable for a study staff member to contact them prior to surgery via phone to clarify if they have any questions. On the day of surgery, if the

PROTOCOL TITLE: Prospective Randomized controlled study comparing liposomal bupivacaine to bupivacaine interscalene blocks for arthroscopic rotator cuff repair surgery

VERSION DATE: 8/5/2020

patient has not already signed consent and is still interested in participating in the study will be presented with consent and Health and Insurance Portability and Accountability Act (HIPAA) forms. The patient will review the forms with the surgeon, research staff, or anesthesiologist. Subjects will be reminded that participation is completely voluntary, and that they may stop participation at any time without question or penalty. The surgeon, research staff, or anesthesiologist will answer any questions that the subjects may have about the study. If the patient decides to participate, they will be asked to sign the consent and HIPAA forms. One copy will be saved for study records, and the subject will be provided with a copy of the forms for their own records.

- Waiver or Alteration of Consent Process: N/A
- Non-English Speaking Participants: N/A- No Non-English speaking patients will be enrolled in this study.
- Participants Who Are Not Yet Adults: N/A
- Cognitively Impaired Adults, or adults with fluctuating or diminished capacity to consent: N/A
- Adults Unable to Consent: N/A

21.0 Setting

21.1 Research Sites: Patients will be consented in the surgeon's clinic or pre assessment clinic. The surgical procedures will take place at the M health Ambulatory Surgery Center or Fairview riverside campus or Fairview Maple Grove Clinics Ambulatory Surgery Center.

21.2 International Research:n/a

22.0 Multi-Site Research N/A

23.0 Resources Available:

Research assistants are available to aid in consent and data acquisition. All research assistants will be familiar with the study protocol and have experience working with similar studies.

We plan to enroll 70 subjects. The plan is to screen 90 subjects to research this target population. This center performs approximately 300 RCRs annually.

PROTOCOL TITLE: Prospective Randomized controlled study comparing liposomal bupivacaine to bupivacaine interscalene blocks for arthroscopic rotator cuff repair surgery

VERSION DATE: 8/5/2020

We plan to conduct this study over 3 months. Enrollment and data collection will be completed at this time. Statistical Analysis will take approximately two months to complete.

All procedures will be performed in the clinical facilities at the MHealth Clinics and Surgery Center and at the West and East Bank. Data storage and analysis will be done using desktop equipment which is available at the Research Office B573 Mayo.

In the event that this research activity results in an injury, treatment will be available, including first aid, emergency treatment and follow-up care as needed. Care for such injuries will be billed in the ordinary manner, to the patient and/or insurance company.

All study personnel will be adequately trained by the Principle Investigator on the study protocol and study conduct. A log will be maintained to track which personnel are trained. A delegation of authority log will also be maintained to track which personnel are responsible for specific duties.

